3. STUDY RATIONALE AND SIGNIFICANCE

Alzheimer's disease is a severe form of memory loss, initially manifesting as mild cognitive impairment and followed by a decline in cognitive function. There is an acknowledged need¹²³ to develop novel disease modifying agents to prevent progressive cognitive decline as patients and health providers are currently without viable pharmaceutical options for this debilitating disease. Concurrently, an interest in alternative therapies has increased substantially over the past two decades, especially among the elderly.¹²⁴⁻¹²⁶ *Centella asiatica* may offer an effective way to bridge this gap, providing a botanical-based therapy to reduce cognitive impairment in Alzheimer's disease.

Centella asiatica shows remarkable cognitive enhancing and neuroprotective properties in extensive preclinical research performed by our group and by others. The small number of human clinical studies favors the use of *Centella asiatica* as a dietary supplement to improve cognitive function and brain health; however, limited regulation of these agents makes efficacy of commercial products unpredictable. Our ultimate goal is to develop an FDA-approved, standardized, botanical extract of *Centella asiatica* for evidence-based treatment of mild cognitive impairment and Alzheimer's disease.

This is the first human pharmacokinetic study of a standardized crude water extract of *Centella asiatica*. Previous pharmacokinetic studies have used refined combinations of *Centella's* unique triterpenes.⁴⁴⁻⁴⁶ Use of such extracts eliminates possible chemical interactions and bioactive synergistic compounds that may result from crude extract preparation. Mouse studies have shown improvements in cognition in wild-type and Alzheimer's disease models using crude water extracts with or without triterpenes^{20,30} suggestive of other neuroactive ingredients within *Centella asiatica* water extract. These appear to include caffeoylquinic acids and potentially other unidentified compounds. This study will preserve possible synergistic effects by using a crude water extract, but also standardize the product to the known bioactive constituents, which has not been done in previous human trials. In addition to studying the triterpenes, this study will investigate the pharmacokinetics and bioavailability of *Centella* derived caffeoylquinic acids and their metabolites, which has not been previously evaluated. The observed pharmacokinetic profile will inform dosage decisions and dosing frequency for future human clinical trials.

3.1. Preliminary data

Centella asiatica water extract is comprised of 0.94-2.41% triterpenes and 0.01-0.46% caffeoylquinic acids.³¹ The abundant triterpenes asiaticoside and madecassoside are known to metabolize to the neuroactive metabolites asiatic acid and madecassic acid *in vivo*.⁴⁹ Similarly, the caffeoylquinic acids metabolize to caffeic acid, ferulic acid, isoferulic acid, and their dihydroderivatives.^{127,128} Working with OHSUs' Bioanalytical Shared Resource/Pharmacokinetic Core (BSR/PKC) we have developed a sensitive methodology using HPLC-MS/MS to separate and analyze the triterpenes, caffeoylquinic acids, and their further metabolites within a human plasma matrix. Linear calibration curves have been obtained for each of these analytes (25–2000 ng/mL for asiatic acid, 5-2000 ng/mL for madecassic acid, and 5-100 ng/mL for several caffeoylquinic acids and their metabolites).

Previous pharmacokinetic literature in rodents and dogs has reported maximum concentrations of the polar caffeoylquinic acid compounds within one hour of ingestion^{128,129} and the less polar triterpenes at 4-5 hours.¹³⁰ We have performed a pharmacokinetic study in wild-type mice on a low phytochemical diet to identify the C_{max} and time to reach C_{max} (t_{max}) of *Centella*'s known bioactive compounds using the standardized water extract. We were able to detect the bioactive caffeoylquinic acids and their metabolites in plasma following oral administration of the extract using reversed phase HPLC-MS/MS (Figure 2, Table 2). Maximum plasma concentrations (C_{max}) of CQAs and metabolites (15 – 2350 ng/ml) primarily occurred within 45 minutes of oral administration (Figure 2) and there were no observable adverse events after extract administration. These results demonstrate *Centella asiatica* water extract is orally bioavailable and well-tolerated in mice warranting further evaluation in humans. They also confirm the proposed metabolism of caffeoylquinic acids from *Centella asiatica* water extract into their respective metabolites. To assess for changes in the bioavailability of the standardized manufactured product to be used for this study (CAP), we will perform another mouse bioavailability study.

[figure not shown]

Figure 2. Pharmacokinetic profile of monocaffeoylquinic acids, dicafeoylquinic acids and metabolites caffeic acid and ferulic acid in wild-type female mice. Six-month-old female mice (n=39) were administered *Centella asiatica* water extract (200 mg/kg) via oral gavage. Four mice were euthanized per time point and blood collected via cardiac puncture for analysis with HPLC-MS/MS.

Table 2. Pharmacokinetic parameters of caffeoylquinic acids and metabolites in mouse plasma after single oral administration of *Centella asiatica* water extract.

Analyte	C_{max} (ng/mL)	t_{max} (min)
Monocaffeoylquinic acids	84.3	15
Dicafeoylquinic acids	37.8	60
Caffeic acid	39.6	15
Ferulic acid	15.2	7.5
Isoferulic acid	2.5	7.5*
Dihydrocaffeic acid	13.1	240*

Dihydroferulic acid	Not detected	Not detected
Dihydroisoferulic acid	124	30*
4-methyl catechol	4.9	120*
4-ethyl catechol	0.94	90*
3-(3-hydroxyphenyl)propionic acid	84.5	7.5*

* Inconsistent time curve

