1. STUDY OBJECTIVES

1.1. Purpose

The purpose of this study is to measure the oral bioavailability and pharmacokinetics of known bioactive compounds from a standardized *Centella asiatica* water extract product (CAP) in

mildly demented elders on cholinesterase inhibitor therapy. Compound levels will be measured in human plasma and urine over 10 hours after acute oral administration of two doses of the botanical extract product. The dose giving maximum plasma levels (C_{max}) closest to those observed in our mouse studies, the area under the curve (AUC_{0-10}), as well as the rate of clearance ($t_{1/2}$) of the known compounds and time of maximum concentration (t_{max}), will be identified. These data will be used to inform decisions on the dosage and dosing frequency for future clinical trials.

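### The mouse Cmax reference for identifying the closest dose is inconsistent (2350 ng/mL in the text of 3.1, at most 124 in Table 2), and no dataset, analyte list or closeness rule is fixed.

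*Combined protocol and SAP*

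**What the plan says.** Section 1.1 lists what the trial will identify, including "The dose giving maximum plasma levels (C_{max}) closest to those observed in our mouse studies", together with AUC, half-life and tmax. These results are to inform dosage and frequency in later trials. Section 10.6 says the human Cmax, tmax and AUC over 10 hours will be compared with the mouse data to judge whether the dosing level is suitable. The Aim 1 hypothesis in 1.4 covers both triterpenes and CQAs and expects that mouse-like plasma levels can be reached.

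The mouse figures are in 3.1. The text reads "Maximum plasma concentrations (C_{max}) of CQAs and metabolites (15 – 2350 ng/ml", closes the bracket, and continues "primarily occurred within 45 minutes of oral administration". Table 2 is headed "Pharmacokinetic parameters of caffeoylquinic acids and metabolites in mouse plasma after single oral administration of" the extract. It has ten detected analytes and one not detected. The lowest row is "4-ethyl catechol 0.94 90" and the highest is "Dihydroisoferulic acid 124 30" (Cmax in ng/mL, then tmax in minutes). Figure 2, which is not visible in the text reviewed, is captioned "Pharmacokinetic profile of monocaffeoylquinic acids, dicafeoylquinic acids and metabolites caffeic acid and ferulic acid in wild-type female mice".

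Section 3.1 also announces a further mouse study with the manufactured product (CAP), to look for changes in bioavailability. It does not say whether that study will supply the reference values.

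**The concern.** A trial that undertakes to say which of two doses comes closest to a reference needs one stable reference and a definition of closest. Here the text and the table, in the same units and for the same class of compounds, disagree about how high the mouse concentrations went. Nothing says which mouse dataset counts, which analytes count, how distance is measured, or what happens if analytes point to different doses.

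The doses differ only 2-fold, so a reference that is wrong by much more than that can determine the answer by itself. If the source and analyte are chosen after the human concentrations are known, the finding on dose becomes a matter of discretion.

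**Working it through.** **Inputs.** Cmax (ng/mL) from Table 2 in 3.1, and the analytes with MS/MS transitions listed for human samples in 9.3:

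| Analyte | Mouse Cmax | In Figure 2 caption | Transition in 9.3 |
|---|---|---|---|
| Mono-CQAs | 84.3 | yes | yes |
| Di-CQAs | 37.8 | yes | yes |
| Caffeic acid | 39.6 | yes | yes |
| Ferulic acid | 15.2 | yes | yes |
| Isoferulic acid | 2.5 | no | yes |
| Dihydrocaffeic acid | 13.1 | no | yes |
| Dihydroisoferulic acid | 124 | no | no |
| 4-methyl catechol | 4.9 | no | yes |
| 4-ethyl catechol | 0.94 | no | yes |
| 3-(3-hydroxyphenyl)propionic acid | 84.5 | no | no |

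**Step 1: try to reproduce 15 to 2350.**
- All ten detected rows: minimum 0.94, maximum 124. Upper end: 2350 / 124 = 19.0.
- The four Figure 2 analytes: 15.2 to 84.3. The lower end of 15 is reproduced (ferulic acid). The upper end is not: 2350 / 84.3 = 27.9.
- A pooled total, bounded above by the sum of all ten Cmax values: 406.84. 2350 / 406.84 = 5.8, so pooling does not explain it.
- A change of unit to nM: the largest value is dihydroisoferulic acid, with an assumed nominal mass of 196. 124 / 196 × 1000 = 633, so this does not explain it either.

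The lower end therefore has an explanation and the upper end has none. The timing statement in the same sentence is sound: six of the ten detected analytes have tmax at or below 45 minutes.

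**Step 2: which analytes could be compared?** The two highest rows of Table 2 (124 and 84.5) have no listed human transition in 9.3. Section 9.3 does list transitions for asiatic and madecassic acid, but the protocol gives no mouse Cmax for either. The set of analytes with a value in both species is not stated and is smaller than either list.

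**Step 3: does the choice matter?** Assume, for illustration, that human Cmax is x after 2 g and 2x after 4 g, and let R be the mouse reference. On the absolute scale the two doses are equally close when R − x = 2x − R, so x = 2R/3.

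- Di-CQAs, R = 37.8: switch at 25 ng/mL
- Mono-CQAs, R = 84.3: switch at 56 ng/mL
- R = 2350: switch at 1567 ng/mL

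On a log scale the switch is at R/√2, giving 27, 60 and 1662 ng/mL. The exact point depends on the distance measure, but the spread between references remains.

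**The case against.** The strongest reply is that 2350 is a slip in a background sentence. A range across different compounds is not a target for any one of them. Comparison with mice has to be made analyte by analyte, and Table 2 prints one Cmax per detected analyte, so no analyte has two competing values in print. Section 1.1 speaks of mouse studies in the plural, another mouse study is planned, and the primary outcome does not use mouse values.

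Much of that stands. What remains is that, if the text is right, either an analyte is missing from Table 2 or a Table 2 value is too low by at least 19-fold. The documents do not say which applies, or whether the text is wrong. The comparison is also a stated purpose in 1.1 and part of the analysis in 10.6, so it needs a usable reference whatever the origin of the slip.

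A reader might infer more than the documents support:
- *That the lower ends also conflict, 15 against 0.94, a 16-fold gap.* The Figure 2 analytes start at 15.2, so this is probably a difference in scope.
- *That only the four rows without an asterisk have a usable Cmax.* The asterisks sit on the tmax entries. An irregular time course may weaken a Cmax, but the table does not flag it.
- *That the mouse values decide the future dose.* They are listed in 1.1 beside AUC, half-life and tmax as information for that decision.
- *That no mouse triterpene data exist.* Table 2 is limited by its title to CQAs and metabolites, so the absence of a triterpene row shows only that no value is reported here.

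**Conclusion.** The point holds in a limited form. The figure of 2350 ng/mL cannot be reproduced from anything in the protocol: it is 19 times the largest Table 2 value and 5.8 times the sum of all ten. The comparison promised in 1.1 and 10.6 also lacks a named dataset, an analyte list and a rule, and it has no triterpene reference although Aim 1 covers triterpenes.

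The effect on the answer is illustrated by switch points of about 25, 56 and 1567 ng/mL. These rest on the assumption that Cmax doubles with dose and on absolute distance. The origin of 2350 cannot be settled from the documents, because Figure 2 is not visible and the source data are not given, although all four of its captioned analytes appear in Table 2 at 84.3 ng/mL or less.

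This should be corrected before analysis. It does not threaten the primary 2 g versus 4 g comparison, and no view is taken on which dose is right.

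**What to change.** 1. Check 2350 in the text of 3.1 against the mouse source data and correct either the text or Table 2.
2. State in 1.1 and 10.6 which single mouse dataset is the benchmark: Table 2 or the CAP mouse study.
3. Limit the benchmark to analytes measured in both species. Add asiatic and madecassic acid if mouse values exist; otherwise say that the comparison covers CQAs and metabolites only.
4. Fix one closeness rule before unblinding. One workable choice is the log ratio of human geometric-mean Cmax to mouse Cmax, reported per analyte for each dose, with the mean absolute log ratio over the list as the summary.

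The cost is a corrected figure and about a paragraph of text, with no new participants, visits or human samples. The drawback is that a single summary can hide disagreement between analytes, so the per-analyte ratios should always be reported beside it. Other rules would serve as well, provided one is fixed in advance.

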3.2 Rationale for exploration of NRF2 activation by CAP in PBMCs

The rationale for this investigation is provided in Appendix 2 of this protocol.

4. RESEARCH DESIGN AND METHODS

4.1. Study design

This is an outpatient open-label phase 1 pilot clinical study using a blinded randomized crossover design of two doses (n=8). Randomization will use an arm equivalence design to promote equal numbers of participants for each order schema. We will dispense a single administration of two different doses (2g and 4g) of a *Centella asiatica* water extract product (CAP) to the participants on two separate occasions two to four weeks apart (Figure 3). Participants will be required to adhere to a “low phytochemical diet” known as a “low plant diet” designed by the Oregon Clinical and Translational Research Institute’s (OCTRI) Bionutrition Department for 48 hours immediately preceding each study visit and for the duration of each study visit. We will provide participants a handout at screening outlining the diet with meal examples. Serial blood samples (2-3 teaspoons; 10 -15 mL/sample) will be obtained through a peripheral intravenous catheter, once prior to *Centella asiatica* consumption and then over a 10-hour post-administration period (15, 30, 45, 60, 90, 120, 150, 180, 240, 360, 480, and 600, and min). Participants will also perform a 10-hour urine collection at each study visit to assess for excretion of *Centella asiatica* metabolites. EKG, measurements as well as kidney and liver function tests will be performed as described in section 6. Adverse events and tolerability will be assessed with questionnaires in-person at each study visit, by phone 24 hours after each study visit, and one week following study completion (Figure 3).

4.2. Outcomes

- Primary outcome:
 - A change in pharmacokinetic parameters (C_{max} and AUC_{0-10}) of plasma analytes after treatment with a product made from a water extract of *Centella asiatica* (CAP) with a detectable difference between doses (2g and 4g).
- Secondary outcomes:
 - The time of maximum concentration (t_{max}) and half-life ($t_{1/2}$) of the known bioactive compounds and their metabolites to help determine dosage intervals
 - Temporal changes in ferric reducing ability of plasma (FRAP) as an indicator of antioxidant potential over time
 - Safety and tolerability of acute doses of CAP determined by participant interviews, biometrics, electrocardiography, laboratory assessments for liver and kidney function, vital signs and questionnaires
 - The level of triterpenes, caffeoylquinic acids, and their metabolites in a pooled urine sample collected over 10 h after CAP administration.
 - Activation of the NRF2 antioxidant response element pathway in peripheral blood mononuclear cells (PBMC) over 6 hours following CAP administration.

[figure not shown]

Figure 3. Study design. *Cognitive assessments: Clinical Dementia Rating (CDR), Mini Mental State Examination (MMSE), Geriatric Depression Scale (GDS); ^Biometrics: weight, height, body mass index (BMI), age, blood pressure, pulse rate, temperature; +Lab measures: complete blood count (CBC), comprehensive metabolic panel (CMP), urinalysis, # comprehensive metabolic panel

4.3. Study Population

4.3.1. Number of participants

Eight mildly demented elderly volunteers on cholinesterase inhibitor therapy (n=4 each female and male) 65-85 years of age will be screened and enrolled in the study. We estimate that we will need to screen approximately twelve potential participants to meet the eight volunteers needed to complete the study. We anticipate a possible dropout rate of 1 participant (14%) However, we are still powered to see differences between doses with a 25% drop out rate resulting in 6 remaining subjects.

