10.6. Specimen analysis

Each CAP derived analyte will be identified by its retention time and characteristic mass spectral fragmentation pattern using selected reaction monitoring. The peak area ratio to the appropriate internal standard will be identified and evaluated against the standard calibration curve of each analyte. Each analyte's concentration will be used to generate a concentration-time curve for pharmacokinetic profiling. Pharmacokinetic (PK) profiling of the triterpenes, CQAs and their metabolites will use non-compartmental analysis (NCA) to calculate common PK parameters such as peak concentration (C_{max}), the time at peak concentration (t_{max}) and the total 10 hour bioavailability represented by the total area under the curve (AUC_{0-10}). These will be compared to the mouse data in order to assess appropriateness of dosing level. Other calculable NCA metrics will also be determined, such as the elimination half-life ($t_{1/2}$) calculated from the profile tails and the mean residency time (MRT) of the compounds in plasma. Descriptive assessment will be done at each of the doses to give basic PK summarization of the various CA compounds and total antioxidant compounds measured by FRAP. NRF2 antioxidant pathway related gene and/or protein levels will be compared in PBMCs from the screening visit, the baseline study visit sample and hourly up to 6h following CAP administration. Dose dependence of the study outcomes will be determined by evaluation of the within-subject differences in study outcomes between the 2g and 4g CAP doses.

Assumptions of normality will be confirmed using outcome density distributions alongside utility from formal tests, such as the Anderson-Shapiro. In instances of normality violation, statistical transformation such as natural logs and square roots will be considered as will non-parametric equivalent tests such as the paired Wilcoxon rank-sum test. Standard diagnostics will be very conservative given the limited number of available subjects but clearly obvious outliers will be removed as necessary. Non-continuous variables such as t_{max} will have frequency distributions compared between doses using chi-square testing. Although all CA compounds of interest and PK parameters are defined a priori, multiple comparison correction to p-values will be applied as necessary, with final two-tail significance defined at $p < 0.05$.

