10.8. Sample size

Sample size was calculated based on the primary outcome measures of C_{max} and AUC. Changes in the response values from the literature were taken from Grimaldi et. al.⁴⁵ for two outcomes, peak concentration (C_{max}) and bioavailability/area-under-the-curve (AUC), at two treatment doses. With respect to C_{max} , estimations from G*Power indicated a sample size of 6 would be sufficient to detect the established criterion difference (critical $t=2.57$).

The post-treatment mean difference in C_{max} from the literature was found to be 0.66 and was replicated during simulation with confidence intervals indicating a significant difference {0.36, 0.96}. Both the observed mean and median test statistics was found to be greater than the critical t (mean $t=4.23$, median $t=3.88$). Mean power was found to be slightly lower than expected (84% versus 86%) although median power was significantly larger (92%). Accordingly, six subjects would be sufficient to detect a difference in C_{max} between two doses of CAP. With the enrollment of 8 subjects, the study will be sufficiently powered even with a dropout rate of 25%.

Similar results were found for bioavailability, as measured as AUC, although at an attenuated effect, with an indicated increase in subject count to a minimum of 7 (critical $t=2.45$). Simulation verified a mean difference of 5.25 that would be expected to be significant based on the simulated confidence intervals {2.43, 8.09}. AUC was also found to be similarly powered, with a mean observed power of 83% and a median power of 93%. Accordingly, a sample size of seven is more than sufficient to meet the proposed criterion for CAP analyte bioavailability. With the enrolment of 8 subjects, the study will be sufficiently powered with 1 dropout (14%). Given the short duration of the study, we expect that a dropout rate of only 1 subject is reasonable. Eight total subjects were proposed for the dose comparison of Aim 1, which would allow for reductions in the detectable shifts of both peak concentration (37% of literature effect; $\Delta C_{max}=0.42$) and bioavailability (31% of literature effect; $\Delta AUC=3.63$) allowing for even greater powering to detect a dose effect of CAP.

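### Section 4.3.1 claims power with six completers, but section 10.8 supports six for Cmax only and requires at least seven for AUC; one dropout of eight is also given as 14% instead of 12.5%

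*Combined protocol and SAP*

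**What the plan says.** Section 10.8 states the basis of the sample size: "Sample size was calculated based on the primary outcome measures of C_{max} and AUC". It then takes the two endpoints in turn.

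- **Cmax:** "estimations from G*Power indicated a sample size of 6 would be sufficient to detect the established criterion difference (critical $t=2.57"). The paragraph concludes that eight enrolled subjects tolerate 25% dropout.
- **AUC:** the effect is weaker, "with an indicated increase in subject count to a minimum of 7" (critical t = 2.45). The conclusion is narrower: "the study will be sufficiently powered with 1 dropout (14"%). The section adds that losing only one subject is a reasonable expectation.

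Section 4.3.1 enrols "Eight mildly demented elderly volunteers on cholinesterase inhibitor therapy (n=4 each female and male"). It anticipates a "possible dropout rate of 1 participant (14%) However, we are still powered to see differences between doses with a 25% drop out rate", with six subjects left. It does not say to which endpoint the claim applies.

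**The concern.** The summary in section 4.3.1 carries the Cmax tolerance over to the whole trial. Six completers is one fewer than the plan's own minimum for AUC, so for one of the two primary endpoints the claim contradicts the calculation behind it. Someone who reads only the section on participant numbers would conclude that two losses leave both primary dose comparisons at planned power.

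The 14% is a separate slip. In section 4.3.1 two adjacent dropout rates use different denominators: 25% is 2 of 8, while 14% is 1 of 7.

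**Working it through.** **Inputs**

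- Two-sided 5% level: "final two-tail significance defined at $p < 0.05" (section 10.6).
- Paired comparison: "evaluation of the within-subject differences in study outcomes between the 2g and 4g CAP doses" (section 10.6).
- Eight enrolled (section 4.3.1).
- Cmax: n = 6, critical t 2.57, mean power 84% against 86% expected, median 92% (section 10.8).
- AUC: n = 7, critical t 2.45, mean difference 5.25, interval 2.43 to 8.09, mean power 83%, median 93% (section 10.8).
- Also in section 10.8: a detectable AUC difference of 3.63 with eight subjects, and 67% AUC power within one gender.
- Not stated: the SD of the within-subject difference and the target power.

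**Step 1. Reproduce the plan's critical values.** For a two-sided paired t-test, t(0.975, n−1) is 2.571 at n = 6 and 2.447 at n = 7. These match 2.57 and 2.45. One-sided values (2.02, 1.94) and unpaired values (2.23, 2.18) do not, so the test is identified.

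**Step 2. Dropout percentages.** 1/8 = 12.5%; 1/7 = 14.3%; 2/8 = 25%. Eight less one leaves 7, which meets the AUC minimum. Eight less two leaves 6, which does not.

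**Step 3. AUC power at six, anchored to power at seven.** Let dz be the mean difference divided by the SD of the within-subject differences. Power is the probability that a noncentral t with n−1 degrees of freedom and noncentrality dz·√n falls beyond ± the critical value. Solve for dz at n = 7, then evaluate at n = 6.

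| Assumed AUC power at n = 7 | dz | Power at n = 6 |
|---|---|---|
| 80% (not in the plan; lower end of range) | 1.273 | 70.4% |
| 83% (the plan's mean AUC power) | 1.325 | 73.8% |
| 86% (the plan's expected Cmax power; upper end of range) | 1.384 | 77.3% |

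**Step 4. Cross-check from the AUC interval.** The half-width is (8.09 − 2.43)/2 = 2.83. Read as a 1.96-type interval at n = 7, SD = 2.83/1.96 × √7 = 3.82 and dz = 5.25/3.82 = 1.37. Power is 85.5% at seven and 76.7% at six, so seven is the smallest n above 80%, as the plan says. Read as a t-interval, SD = 3.06 and dz = 1.72. Five subjects would then reach 81% and six 91%, which does not fit a minimum of seven.

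**Step 5. What a minimum of seven implies.** If the target is 80% (an assumption), dz must lie between 1.273 and 1.435 for seven to be the smallest sufficient n. Power at six is then at least 70.4% and below 80%.

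**Step 6. Other AUC figures in section 10.8.**

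| Figure used | Reading | dz for 5.25 | Power at n = 6 |
|---|---|---|---|
| Median power 93% | at n = 7 | 1.57 | 86% |
| Detectable difference 3.63 | n = 8, assumed 80% power: dz = 1.156, SD = 3.63/1.156 = 3.14 | 1.67 | 90% |
| 67% within one gender | paired, n = 4 | 1.79 | 93% |

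Conversely, dz = 1.325 gives only 45% at n = 4, against the stated 67%. The AUC figures in section 10.8 therefore do not come from one common SD under these readings.

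**The case against.** The strongest reply is that the shortfall cannot be quantified. The SD and the target power are unstated. Only the 83% in the first table is an AUC power from the plan, and three other figures in the same section put power at six between 86% and 93%. A reader might infer from the 74% that AUC power with two dropouts is known to fall short by a set amount. The documents do not support that, and 74% should not enter the protocol as a fact. This part of the reply stands.

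It does not remove the contradiction. The plan set the AUC minimum at seven. If the more favourable figures are right, that minimum needs explaining; if the minimum is right, section 4.3.1 is wrong for AUC.

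It is also fair that section 10.8 already separates the endpoints and limits AUC to one dropout. The main edit therefore belongs in section 4.3.1; section 10.8 needs the percentage corrected and its figures reconciled.

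Finally, the consequence is modest. This is a two-visit phase 1 pilot that expects one dropout, and the gap opens only with two or more. A reader might go further and infer that the trial is underpowered for AUC, or that enrolment must rise (keeping seven after 25% loss would take 7/0.75 = 9.33, so 10). The documents support neither: eight enrolled with one lost meets the stated minimum for both endpoints.

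**Conclusion.** The point holds as an internal contradiction. By the plan's own minimums, the loss that both primary endpoints can absorb is one of eight (12.5%); two of eight (25%) is supported for Cmax only. The 14% in both sections should be 12.5%; this slip has no effect on the design. These conclusions rest on stated figures and simple arithmetic, so confidence in them is high.

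Confidence in the size of the AUC loss is much lower. It is about 74% at six if 83% at seven is accepted, and 70% to 77% for 80% to 86% at seven, under a paired t-test with an SD inferred from that power. The competing figures of 86% to 93% do not fit the minimum of seven, and only the sponsor's statistician can resolve this.

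**What to change.** - **Section 4.3.1:** state that one dropout (12.5%) preserves the planned power for both primary endpoints, and that with two dropouts (25%, six remaining) it holds for Cmax only.
- **Sections 4.3.1 and 10.8:** change 14% to 12.5%.
- **Section 10.8:** the sponsor's statistician should give the SD actually used and the resulting AUC power at six, and reconcile with the minimum of seven the 93% median power, the 3.63 detectable difference and the 67% within-gender power.

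The cost is a few sentences and one recalculation from inputs the sponsor should already hold. One stated design property becomes less favourable; sample size, conduct and analysis are unaffected.
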